At least 15% of people are clinically obese at the time of MS diagnosis.¹ Obesity is also a risk factor for the conversion of radiologically isolated syndrome (RIS) (early MS) to first attack and negatively influences MS functional outcomes and disability.²⁻⁴ Ocrelizumab is increasingly the disease modifying treatment of choice for people with MS in the USA and globally. Many Ocrelizumab-treated patients are starting to administer (with or without physicians' guidance) the glucagon-like peptide-1 (GLP-1) agonists⁵, such as semaglutides, for diabetes, weight loss, and an increasing number of FDA-approved and experimental indications. Many other patients with MS would like to start this drug class to induce weight loss. Others may be influenced by early phase data that suggest the GLP-1 medication class is neuroprotective, reduces cardiovascular disease risk, and/or allows weight maintenance to return to regular aerobic physical activity.⁶⁻⁸

Study Significance and Motivation

Although there is growing interest in understanding how metabolic interventions may intersect with immunotherapies in MS nearly no data exist on the co-treatment of people with MS with Ocrelizumab and a GLP-1 agonist (e.g. Wegovy). In 2023-24, we performed a small, retrospective study of ~50 people with MS and their weight loss and tolerability of GLP-1 agonists in Boston, many of whom were treated with Ocrelizumab (Udawatta et al. *Neurology Sci.* 2024 doi: 10.1007/s10072-024-07701-7).⁹ Others have followed with observational data on GLP-1 in cohort studies or have work in progress.^{10,11}

However, the sample sizes in existing published work are so far too small to conclude the outcomes of MS patients treated specifically with Ocrelizumab. Also, patient-based assessments and reports were lacking as early work has been largely retrospective and spanning the time when the GLP-1 agonists were only approved for MS patients with comorbid diabetes mellitus.

RESEARCH DESIGN AND METHODS:

Study Aims

In this prospective study, there are two main aims:

- (1) To implement patient-reported outcome measures (PROMs) in **60** people with MS already treated with both Ocrelizumab and a GLP-1 agonist to assess progression and ambulation, while recording drug tolerability and potential adverse events, weight loss, disease-based outcomes focused on progression, and MS-focused quality of life; and

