- (2) Enroll a single-arm, open-label trial of **40** Ocrelizumab-treated MS patients who are soon starting GLP-1 agonists, monitored prospectively for 2 years to measure MS **progression** (clinical disability worsening, stability or improvement) every 3 months, including (a) clinical assessments (e.g. EDSS, 25-foot timed walk, SDMT) as used in the ORATORIO trial of Ocrelizumab, (b) PROMs on progression in MS including fatigue, ambulation distance, mood; and (3) simple objective biomarkers of disease (e.g. plasma neurofilament light chain, glial fibrillary acidic protein).

Overview: Aims 1 and 2 will recruit participants simultaneously but draw upon MS participants at different points in their GLP-1 agonist treatment. Participants can enroll in either the cohort of Aim 1 (in-person or remote) or the open label trial of Aim 2 (in-person only), not both aims. All participants will be Ocrelizumab-treated for MS upon study enrollment.

Study Endpoints

The primary outcome measure is **PIRA** (progression independent of relapse activity), based primarily on clinical assessment, dichotomized as present or not.¹²

For Aim 1, the cohort, patient-derived disability status (PDDS) score, and ambulation score (self-reported) will be the primary endpoints of interest.

For Aim 2, the clinical trial, PIRA will be measured pre-GLP-1 start and at study end (week 72). A composite score of disability, similar to the ORATORIO¹³ trial will be constructed including EDSS score, 25-foot timed walk, 9-hole peg test, and SDMT score.

Study Interventions/ Investigational Agent

Glucagon-like peptide-1 agonist agent is the study agent of interest. This study will not supply the GLP-1 drug but depend on the patient's clinical prescription of this drug. Similarly, all participants will be treated with Ocrelizumab for the indication of MS; however, the study will not provide Ocrelizumab as it will be part of the participant's routine clinical care.

Study Procedures

Inclusion Criteria, Aims 1 and 2:

- 1) Diagnosis of MS (2019 revised McDonald criteria) of any type (PPMS, RRMS, SPMS) by a neurologist,
- 2) Adult age 18-70 years,
- 3) BMI $\geq 24.0 \text{ kg/m}^2$,
- 4) Taken at least one dose of Ocrelizumab prior to study entry,
- 5) EDSS < 7.0 ,
- 6) Able to provide individual informed consent,
- 7) MRI available to confirm the diagnosis of MS.

Exclusion Criteria, Aims 1 and 2:

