- 1) Prior exposure to Mavenclad, Lemtrada, Cyclophosphamide, stem cell transplant or related bone marrow suppressive treatment,
- 2) Current clinical trial participant,
- 3) Unable to speak a language for which translation can be found in the hospital system,
- 4) Unclear documentation of MS diagnosis or prior or current MS treatment,
- 5) Relapse within the past 3 months,
- 6) Recent major surgical procedure in the past 6 months,
- 7) Exposure to steroids (systemic) within the past 3 months,
- 8) Not on Ocrelizumab in the past > 9 months,
- 9) Moribund status,
- 10) Underweight or experiencing protein malnutrition,
- 11) Unable to provide consent voluntarily due to reasons of capacity or other reasons (e.g. incarcerated, dementia, etc.),
- 12) Unable to complete the study activities for any reason as deemed by the study investigator.

*Additional Inclusion Criteria Aim 1:

- 8) Exposed to GLP-1 agonist treatment in the last 3 years or less, or starting on a GLP-1 agonist in the coming < 3 months,
- 9) Willing to report monthly patient-reported outcomes remotely or in-person.

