***Additional Inclusion Criteria Aim 2:**

- 8) Able to present for baseline and follow up in person,
- 9) Unexposed to a GLP-1 agonist in the past year,
- 10) Starting on a GLP-1 agonist in the next <6 months,
- 11) Plan to be exposed to GLP-1 agonist for a minimum of 72 weeks following enrollment.

Participant Population(s)

Accrual Number:	Category/Group:	Consented/Enrolled:
Local	Individuals with MS already treated with Ocrelizumab and GLP-1 agonist	60
	Ocrelizumab-treated MS patients initiating GLP-1 agonist	40
Study-wide		
Total:		100

RECRUITMENT METHODS:

Potential participants will be identified through online research advertising webpages (e.g., ClinicalTrials.gov, Northwestern's clinical trials website), the investigator's connections with MS neurologists in the practice and surrounding practices, advertisements in MS clinics, the National MS Society local chapter's and national websites, MS physician networks, social media directly to patients, flyers in the medical infusion center, weight loss and nutrition clinics in the region, and through clinic newsletters and the word of mouth.

Interested patients will be screened through an online RedCap™ form for the study's eligibility criteria. Medical records review will occur by the investigators to ensure the criteria are met. Participants will then be called by telephone or met in person to describe the study procedures in detail.

CONSENT PROCEDURES:

Consent will be taken by a trained study team research coordinator or physician. All consent will be written on a standardized consent form, in English. Consent may be performed electronically using REDCap e-sign with an institutionally approved account. Participants will be given >24 hours to review the consent form and provide consent. Given the complexity of the study tasks including multiple self-reported variables, only participants who are able to provide their own consent will be enrolled.

Vulnerable Populations

Vulnerable populations will not be enrolled. Participants who lack capacity to voluntarily consent (e.g. institutionalized, dementia) are excluded as per the criteria listed above.

STUDY PROCEDURES:

Aim 1 will allow fully remote participation, drawing from geographically diverse settings throughout the USA. Participants in Aim 1 do not need to visit the study site in person or be

independently mobile but must be continuously available during the study timeframe remotely for PROMs and study surveys and calls.

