Participants will be enrolled for an estimated 72 weeks: Measurements will be requested every four weeks (i.e. q28 days) on a specifically designed survey instrument for MS participants. Participants will be asked to report medication dosing, adherence to medicine, tolerability, weight, height, and exercise activities. Self-reported scales will be administered to the participants as well (measuring disability, fatigue, mood, and quality of life).

Participants must be currently on Ocrelizumab (last dose within the past <6 months) and currently taking a GLP-1 medication.

Participants will be contacted and interviewed via Zoom every 6 months to ensure study procedures are going as planned, verify data reported on medication and MS disease history, and ensure study procedures are operating smoothly. Participants who do not complete the surveys within 7 days of the scheduled timing will be contacted by a study coordinator by phone up to 3 times. Participants will also be asked to report any medication changes, dose changes, or discontinuations if they occur at any point between study visits.

Participants will be enrolled until a total of 40 individual participants are reached. Study procedures for each group are listed in Tables 1 and 2. All scheduled events will be part of the study and not part of routine clinical care.

Table 1: Measurements of MS Participants in Aim 1 (Cohort): Frequency and Scale

Measure	Frequency of Reporting	Scale
Weight	Monthly	kg or lbs
Height	Baseline	cm or inches
Waist, Hip, Limb Circumferences	Monthly	cm or inches
Ambulation score	Monthly	Kurtzke Scale
Disability Score	Monthly	PDSS
Step Count	Monthly	Average daily number on phone or step counter if available
Fatigue	Monthly	Fatigue Severity Scale
Mood	Monthly	Beck Depression Inventory
Quality of Life	q3 months	MS-QOL-54 survey
Intolerabilities	Monthly	Self-reported, qualitative, categorized – gastrointestinal, injection site, infections, etc.
Adherence	Monthly	Number of doses taken/ Total Prescribed doses of GLP-1
Axonal degeneration	Baseline and end of study (if possible)	Neurofilament light chain (serum)
New attacks or lesions	Ad hoc	Reported event if occurs

Table 2: Measurements of MS Participants in Aim 2 (Single-Arm Open-Label Trial)

	Screening	Baseline	Week 24	Week 48	Week 72	Unscheduled Visit (e.g. Relapse, Early Withdrawal)
Clinical & MS Relapse History	X	X	X	X	X	X

Medication Review	X	X	X	X	X	X
Physical Examination	X		X	X	X	X

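### Aim 1's GLP-1 entry rules conflict for people about to start the drug, and its procedures carry an unlabelled stop number of 40 against a target of 60

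*Protocol*

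**What the plan says.** **GLP-1 status at entry to Aim 1**
- Study Aims describes the cohort as "people with MS already treated with both Ocrelizumab and a GLP-1 agonist". The accrual table under Participant Population(s) labels the group of 60 "Individuals with MS already treated with Ocrelizumab and GLP-1 agonist".
- Additional Inclusion Criteria Aim 1, criterion 8, reads "Exposed to GLP-1 agonist treatment in the last 3 years or less, or starting on a GLP-1 agonist in the coming < 3 months".
- The Aim 1 text under STUDY PROCEDURES requires current Ocrelizumab treatment "and currently taking a GLP-1 medication".
- Allocation and Blinding states that every participant will be treated with both drugs.

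**The neighbouring Aim 2 group**
- The accrual table calls the group of 40 "Ocrelizumab-treated MS patients initiating GLP-1 agonist". Its additional criteria 8-11 require in-person attendance, no GLP-1 exposure in the past year, "Starting on a GLP-1 agonist in the next <6 months", and a plan for at least 72 weeks of exposure.
- The Overview under Study Aims says the two aims "draw upon MS participants at different points in their GLP-1 agonist treatment" and that nobody may join both.

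**Enrolment number**
- Study Aims and the accrual table give 60 for Aim 1 and 40 for Aim 2. The study summary gives 100 in all.
- The STUDY PROCEDURES text opens with Aim 1 and covers remote participation, four-weekly surveys and Zoom interviews. It then says "Participants will be enrolled until a total of 40 individual participants are reached".
- Study Timeline plans 4-6 people per month for about 12-15 months in Aim 1, and 3-4 per month for about 12 (up to 18) months in Aim 2. Recruitment runs until both groups reach target.

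**The concern.** Screening staff need one entry rule and one stop number, and for Aim 1 the protocol gives two of each as written.

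The entry rule matters more. The two rules recruit different people, and the future starters admitted by criterion 8 are the same kind of person as Aim 2's initiators. The choice also affects a reported result. The Aim 1 analysis text reports weight change as the last value minus the first. For a current user the first value is measured on drug; for a future starter it is measured before the drug. A summary that mixes the two has no single meaning.

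The number matters because it stands in the section that staff would follow for Aim 1. Taken literally there, it would stop the cohort 20 people short.

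**Working it through.** **Step 1. Which aim does the current-use requirement govern?** Aim 2 criterion 9 requires no GLP-1 exposure in the past year, so a requirement to be on the drug now cannot apply to Aim 2. It is an Aim 1 rule.

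**Step 2. Apply both Aim 1 rules to each type of candidate.**

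| Candidate | Criterion 8 | STUDY PROCEDURES | Described as already treated |
|---|---|---|---|
| Current user, started within 3 years | passes | passes | yes |
| Starting in under 3 months, no earlier use | passes | fails | no |
| Former user, stopped within 3 years | passes if read alone | fails | arguable |

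The second row is a direct conflict. The third depends on how the two passages are combined.

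**Step 3. Overlap with Aim 2.** A start within 3 months lies inside Aim 2's window of under 6 months. If that person is also unexposed for the past year, can attend in person and plans at least 72 weeks of exposure, Aim 2's additional criteria 8-11 are met. The person then fits both aims if willing to give Aim 1's monthly reports. The Overview forbids joining both but does not allocate the person.

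**Step 4. Pre-drug follow-up of a future starter.** Aim 1 lasts an estimated 72 weeks with four-weekly reports: 72 × 7 = 504 days, and 504 / 28 = 18 follow-up reports. For a start just under 3 months after entry (taken as about 91 days), the reports at days 28, 56 and 84 come before the first dose: 3/18 = 17%. This is the most for one such person. The number of such people is not given.

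**Step 5. Enrolment number.**
- Stated total: 60 + 40 = 100, which reproduces the study summary. With 40 in Aim 1 it would be 40 + 40 = 80.
- Aim 1 pace: 4 × 12 = 48 to 6 × 15 = 90 people.
- At 60: 60/6 = 10 to 60/4 = 15 months. Filling 12-15 months needs 60/15 = 4.0 to 60/12 = 5.0 per month, inside the target.
- At 40: 40/6 = 6.7 to 40/4 = 10 months. Filling 12-15 months needs 40/15 = 2.7 to 40/12 = 3.3 per month, below the target.
- By dates: the first Aim 1 participant is due within 30 days of 15 September 2025, so by 15 October 2025, and enrolment is to end on 31 December 2026. That is 442 days, or 14.5 months. 60/14.5 = 4.1 per month; 40/14.5 = 2.8 per month.
- Aim 2 pace: 40/4 = 10 to 40/3 = 13.3 months, which agrees with about 12 (up to 18) months.

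The figure 40 fits Aim 2 and does not fit Aim 1.

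**The case against.** **The number is only a slip.** The sentence names no aim, and the next one refers to each group and to both tables, so the paragraph may be a bridge to both aims. Every explicit statement of the Aim 1 target is 60. This largely stands. A reader might infer that Aim 1 has really been cut to 40, but the total and the timeline point the other way. The timeline does not prove it, since the pace is a target and the duration approximate. The sentence still needs a label, because everything before it in that section concerns Aim 1.

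**The two entry passages can be read together.** Exposure in the last 3 years and current use can both be required, so the procedures text narrows that limb without contradicting it. That is a fair reading. A reader might infer that former users will be enrolled and give all 18 reports off drug. The documents do not support this: it needs criterion 8 read alone, and Allocation and Blinding says that all participants will be treated with both drugs. The cumulative reading does not rescue the future-starter limb, because someone who has yet to start is not currently taking the drug.

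**The overlap harms no planned comparison.** Nothing is randomised, the analysis text sets out no contrast between the aims, and the overlap is narrowed by Aim 2's 72-week requirement. This stands. A reader might infer that the overlap biases a between-aim comparison, but none is planned. What remains is an unallocated type of participant and an ambiguous starting weight.

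**Conclusion.** The point holds in two parts.

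1. **Entry rule.** The future-starter limb of Aim 1 criterion 8 contradicts the current-use requirement in STUDY PROCEDURES and does not match the already-treated description in Study Aims and the accrual table. The limb on exposure in the last 3 years is broader than the procedures text but can be reconciled with it. The effect is up to 3 of 18 reports before the first dose for each future starter (assuming 3 months is about 91 days), plus a starting weight of mixed meaning. The effect on the cohort as a whole cannot be computed, because the share of future starters is unknown.
2. **Number.** 40 against 60, a gap of 20 people, most likely Aim 2's target left unlabelled. On its own this is editorial.

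Both should be corrected, and the first carries the weight. A reader might go further and fault the Aim 1 tolerability rate for counting all observed time. The protocol states that rate clearly and it is a valid summary, so that is no part of this point.

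**What to change.** - Restate the enrolment sentence in STUDY PROCEDURES with a number for each aim: 60 for Aim 1 and 40 for Aim 2.
- Before recruitment, or by amendment, reconcile Study Aims, Additional Inclusion Criteria Aim 1, the accrual table and STUDY PROCEDURES to one GLP-1 entry rule for Aim 1. Which rule is for the investigator to decide; this review does not choose.
- In doing so, make plain whether the limb on exposure in the last 3 years is meant to be read together with current use.
- If people not yet on drug stay eligible for Aim 1, state which aim takes someone who meets both sets of criteria, and report these people separately in Aim 1, at least for weight change.

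The cost is wording in a few places and one extra breakdown in the Aim 1 report. No new visits or data items are needed. A narrower entry rule, if that is the choice, could slow Aim 1 recruitment. There is little slack: 60 people in 14.5 months already needs 4.1 per month against a target of 4-6.

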Participants who discontinue GLP-1 agonist drugs for any reason, including tolerability, cost, desired weight loss outcome, etc., will continue to be observed until the end of the study period. It is possible that participants will have periods of discontinuation and then resume GLP-1 agonist treatment. The participant will be observed until (a) week 72 visit (i.e. end of study period), (b) participant withdrawal with no consent to continue monitoring, or (c) investigator-decided withdrawal of a participant from the study (e.g. severe medical illness preventing study completion, departure far from study site, etc.).

Participant Compensation for Involvement in Research Procedures

Aim 1: Each participant will receive 75 USD every 3 months with a total of up to **600 USD**.

Aim 2: Each participant will receive 150 USD at baseline and 100 USD every subsequent visit occasions and then 150 USD at the final study visit with a total of up to **500 USD**.

Participants will have the option to receive cash or a gift card. Participants who receive cash will need to provide their social security number for the reporting of taxable income to the Internal Revenue Service, according to applicable laws.

There is no anticipated drug development or future product anticipated in this study. A study participant will not have any right to compensation or ownership interest related to such development.

RISKS AND BENEFITS:

Risks to Participants

Participants in this study may have side effects of the medications under investigation including both Ocrelizumab and the GLP-1 medication, although these will be given in the context of clinical care for U.S. Food and Drug Administration (FDA)-approved indications. In particular, the GLP-1 class of medications is known to cause gastrointestinal symptoms, including nausea, vomiting, early satiety, and abdominal discomfort. These are considered reversible, common (approximately 1/3 of all people treated with a GLP-1 medication), and expected. These risks are often mild to moderate and in some cases may lead to early discontinuation of the medication if poorly tolerated. Participants may experience injection-site reactions which could be bothersome.

An additional risk is that participants will be psychologically burdened by repeated testing and surveying throughout the study; however, no clinical harm is anticipated from surveys or the clinical assessments done during the study procedures.

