Participants will have access to their personal study results at the end of the study after the data are locked and the data are presented, including their clinical scores and their biofluid test results. Future test results, if additional tests are performed on stored blood samples, will be reported back to individual participants only if the test results provide a possibility of clinical relevance to the participant.

There will be no interim results reporting to participants. This is to avoid potential biases in the study as many variables are self-reported.

Data Management and Confidentiality:

The data will be kept in a secure file and analyzed using software that included password protections, encryption, and related security features. Computers will be stored in locked offices. All participants will be given unique study identifiers that they will have throughout the study period. A master file of the participants' personal information and unique identifiers will be kept separately from the study's data collection processes online. Data will be transmitted only using institutional software and secure means such as RedCap that has appropriate institutional security features.

Data will be collected online using RedCap using surveys with forced responses before survey completion to minimize missingness of data. Data will be exported to Microsoft Excel and analyzed using statistical software (e.g. R programming language). Surveys will be scored by the study team using the validated, published metrics (e.g. EDSS, FSS, MS-QOL-54). Variables

of interest will be graphed for distribution (i.e. normalcy) and skew. There will be no data imputation. Missing data will be considered missing completely at random. Interim data analyses will occur every 6 months for reporting to the sponsor. A *p*-value of <0.05 is considered statistically significant.

Aim 1:

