Variables of interest will be reported using descriptive frequency-based statistics (e.g. mean, median, range). Subgroups of interest (e.g. by gender, disability level below or above the median, etc.) will be compared using t-tests and tests of two proportions as appropriate. Repeated measures (e.g. weight) will be graphed and displayed. Change in values will be reported (final minus starting weight). If needed to report an outcome, repeated measures analyses, will be made using generalized linear models. Incidence of tolerability issues will be reported as the number of events per number of person-months of observation available.

Aim 2:

This will be an intention to treat analysis. All participants who enroll in the single-arm study will be analyzed to the end of their study participation, either the end of the planned study period or time of withdrawal. Data will be analyzed in aggregate with descriptive subgroup analyses performed with the following variables and subgroupings of interest: (1) sex at birth, (2) age at enrollment below or above the median age, (3) duration of GLP-1 (72 weeks versus early discontinuation), (4) BMI group (<30.0 kg/m², 30-39.9 kg/m², >40.0 kg/m², and (5) EDSS score at enrollment above or below the median.

The primary outcome measure is PIRA, dichotomized as present or not, as measured by the rater-determined composite functional outcomes score. This includes the EDSS score with contributions by the 9-hole peg test, SDMT, and 25-foot walking test, and will be constructed as presented in the ORATORIO trial for Ocrelizumab in primary progressive MS vs. placebo.

EDSS will be measured pre-GLP-1 (enrollment) and at the participant's end of study (i.e. one of (a) the end of planned study enrollment period, (b) administrative withdrawal, or (c) participant withdrawal). A positive change in EDSS score of 1.0 points with a baseline EDSS of <5.0 or a positive change in EDSS score of 0.5 points or more with a baseline EDSS score of 5.0 or higher will be considered PIRA. EDSS will be captured at each study visit but the first and last EDSS scores will contribute to the assessment of PIRA for the primary study outcome's hypothesis testing. The use of the EDSS scores at each q24week study visit will also be used in a generalized linear model to determine disability level worsening at any timepoint.

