Variables that will be collected or measured, as potentially related to the endpoints of interest, include: subtype of MS (relapsing remitting, primary progressive, secondary progressive), prior DMT use (number of prior DMTs, names), history of relapse of MS in the prior 1 year, highest body weight in the prior year, average body weight in the preceding year, comorbid diagnoses (diabetes mellitus, cardiovascular diagnoses, psychiatric (present/absent, duration)), concomitant medications (particularly those that may affect body weight), smoking status (cigarette), alcohol intake (amount), etc.

Regression variables of interest for the outcome of PIRA will be assessed using exploratory univariate regressions of individual variables of interest. These variables will be determined *a priori* and include sex assigned at birth, age at baseline, BMI at baseline, EDSS at baseline, duration of MS disease (from diagnosis), duration of Ocrelizumab (Ocrevus) treatment.

Secondary endpoints will include (1) a change in 25-foot timed walk, (2) MS-QOL-54 scores, and (3) neurofilament light chain levels.

Sample size justification: The proportion of people with PIRA on GLP-1 agonist drugs and Ocrelizumab is unknown. The proportion of patients with PIRA in relapsing MS ranges up to 24% in published reports.¹⁴ In this study, the detectable difference between a known proportion of patients with PIRA and our study group is $\geq 10\%$, with alpha=0.05 and power=0.8. Since participants will not be randomized to no treatment or intentionally discontinued on GLP-1 agonist treatment during the study, there is no comparison group.

All approved data storage platforms, back-up and recovery procedures, and data access controls will be performed in accordance with the data storage policy at Feinberg School of Medicine: <https://www.feinberg.northwestern.edu/it/policies/file-storage.html>

Provisions to protect the privacy interests of participants:

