The submission of ethics board approvals will take approximately 4 months and will be submitted by no later than June 30, 2025. The anticipated start date of the study will be September 15, 2025. Recruitment processes for both study participant groups (Aims 1 and 2) will occur simultaneously. The first patient in for Aim 1 is anticipated within 30 days and the first in for aim 2 is anticipated within 60 days of study start. Recruitment will continue until the target participant enrollment number is reached in both study groups. The enrollment pace will be set not to exceed 6 people per month for Aim 1 to ensure study procedures are robust, with a target of 4-6 people per month. Aim 1 will take approximately 12-15 months to enroll. The anticipated time to complete the enrollment of Aim 1 is December 31, 2026. Aim 2 will take an estimated 12 (up to 18) months to enroll with an anticipated enrollment of 3-4 participants per month. Aim

2 will also complete enrollment in approximately December 2026. Each participant will be followed for 72 weeks. It is anticipated that the last participant out (Aim 2, and complete study) will be April 2028. The final data cleaning and analysis will take approximately 4 months. Interim results will be available to the sponsor at defined intervals before the final study report, at approximately every 6-month intervals. The final study results will be compiled into reports and manuscripts by spring 2028 with study closure in approximately summer 2028.

Qualifications to Conduct Research and Resources Available

The Principal Investigator is a board-certified neurologist with a PhD in International Health Epidemiology. She has over 11 years of experience in neuroimmunology and has served as the lead investigator on multiple clinical trials and observational studies focused on multiple sclerosis.

The research team includes trained clinical research staff who have completed all required certifications, including Good Clinical Practice (GCP), CITI Program training, and other protocol-specific qualifications relevant to this study. All study personnel will receive thorough training on the study protocol, the informed consent process, and ethical considerations to ensure the safety of the participants.

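### The blanket no-imputation, missing-completely-at-random rule understates worsening on the Aim 2 timed-walk endpoint when a participant can no longer do the walk because of MS

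*Protocol*

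**What the plan says.** The missing-data rule stands in the protocol under Data Management and Confidentiality, before the separate Aim 1 and Aim 2 paragraphs: "There will be no data imputation. Missing data will be considered missing completely at random". It makes no exception by endpoint or by reason.

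The Aim 2 text under the same heading names the endpoint: "Secondary endpoints will include (1) a change in 25-foot timed walk", followed by MS-QOL-54 scores and neurofilament light chain. Table 2 schedules the walk at baseline and at weeks 24, 48 and 72.

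Aim 2 is an "open-label trial of 40 Ocrelizumab-treated MS patients". The inclusion criteria admit MS "of any type (PPMS, RRMS, SPMS) by a neurologist" with EDSS below 7.0, and the Study Timeline says "Each participant will be followed for 72 weeks". On the analysis set, the Aim 2 text promises intention to treat: "All participants who enroll in the single-arm study will be analyzed to the end of their study participation". The protocol gives no category, cap, rank or score for a walk that a participant is unable to perform.

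**The concern.** Data are missing completely at random only if the chance of being missing has nothing to do with the values, seen or unseen. A timed walk not done because the participant has lost the ability to walk the distance fails that condition in the plainest way, since the value is absent because the outcome was bad. On a performance test, inability is a result, and the worst one.

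Followed as written, the rule gives such a walk no value, forbids assigning one, and treats its absence as uninformative. The participants who did worst on the endpoint then leave its analysis. Because the study has a single arm, the loss cannot be balanced by a similar loss in a control group. The same person could be recorded as progressed on EDSS and contribute nothing to the walk result, so the two could appear to disagree.

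**Working it through.** The protocol gives no standard deviation, expected change, expected missingness or power for the timed walk, so there is no stated figure to reproduce. What can be checked is whether the case can arise, which way the error runs, and how large it is on assumed inputs.

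**1. Can it arise?** Eligibility includes primary and secondary progressive MS and EDSS values up to just below 7.0. The extra Aim 2 criteria require in-person attendance, not the ability to walk 25 feet. Follow-up is 72 weeks. Nothing keeps out people close to losing the walk.

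**2. Do the protocol's safeguards help?** Data capture relies on "surveys with forced responses before survey completion to minimize missingness of data". That works for questionnaires but cannot produce a time for a walk that was not done. The withdrawal criteria also foresee "severe medical illness preventing study completion", so the protocol itself expects some health-related missingness, although the point here does not depend on it.

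**3. Direction.** Let N be the number enrolled, W the number who truly worsened, and k the number among those W who cannot do the walk.

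- Counting inability as worsening: W/N
- Dropping those participants: (W − k)/(N − k)
- Understatement: W/N − (W − k)/(N − k) = k(N − W)/[N(N − k)]

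The understatement is positive whenever k > 0 and W < N, so this mechanism can only lower the apparent worsening.

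**4. Size as a proportion (illustration).** N = 40 is from the protocol. W = 8 (20%) and k = 1 to 4 are assumptions.

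| k unable | Complete-case | Inability counted | Understatement (points) |
|---|---|---|---|
| 1 | 7/39 = 17.9% | 8/40 = 20.0% | 2.1 |
| 2 | 6/38 = 15.8% | 20.0% | 4.2 |
| 3 | 5/37 = 13.5% | 20.0% | 6.5 |
| 4 | 4/36 = 11.1% | 20.0% | 8.9 |

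Check for k = 4: 4 × 32/(40 × 36) = 128/1440 = 8.9 points.

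**5. Size as a mean change (illustration).** The endpoint is worded as a change, so a second set of assumptions was simulated: 4,000 trials of 40 participants, change in log walk time normal with mean 0.08 and SD 0.25, with the participants who slowed most taken as unable to walk. Mean slowing in the full data is about 8.3%, which agrees with exp(0.08) − 1. Dropping the worst 2.5%, 5% and 10% (1, 2 and 4 of 40) gives 6.8%, 5.5% and 3.3%. None of these simulation inputs comes from the protocol.

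**The case against.** The strongest reply is that the protocol never says an inability is recorded as missing. Coding a test as unable to perform is a scoring or case-report-form convention, distinct from imputation, and could be left to an analysis plan or manual that is not at hand. It is true that the exclusion is inferred from the general rule. But the rule is stated without exception. As it stands, a later document that assigned a worst value to a walk with no recorded time would be open to the charge of contradicting it. The wording needs an exception.

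A second reply is that participants are analysed to the end of their participation, so the last completed walk might be used. That would still omit the loss of walking, and carrying a value forward is itself hard to square with a ban on imputation.

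A third is that this is one secondary endpoint with no stated power, and the number affected is unknown and could be zero. That stands, and it limits the weight of the point.

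Several stronger readings are tempting but not supported:

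- **That the primary outcome is biased in the same way.** The PIRA rule uses the first and last EDSS, which can still be scored when walking is lost. From a baseline of 5.0 or higher, a rise of 0.5 already counts.
- **That the composite or the 9-hole peg test is affected.** The composite is to be built as in a cited trial whose handling of inability is not at hand, and the peg test is not among the listed secondary endpoints.
- **That reaching EDSS 7.0 by itself makes a 25-foot walk impossible.** The protocol does not define the EDSS steps, and the argument does not need this.
- **That the error can be measured against the 10% detectable difference.** That figure concerns the PIRA proportion, not the walk.

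**Conclusion.** The point holds for the timed-walk endpoint. Treating a walk not done because of MS as ignorable missing data is untenable, and the error runs one way, towards less apparent worsening. The size cannot be obtained from the protocol, which gives neither a baseline EDSS distribution nor an expected rate of losing the walk. With 20% truly worsened and 1 to 4 of 40 unable to walk, both assumed, the reported proportion falls to between 17.9% and 11.1%. The protocol does not define a walk responder rate, so these proportions illustrate scale and do not predict what will be reported. This should be corrected, but it does not threaten the EDSS-based PIRA result.

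**What to change.** Under Data Management and Confidentiality:

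1. Limit the no-imputation and missing-completely-at-random statement to tests missed for reasons unrelated to MS.
2. Record a reason code for every scheduled walk not done.
3. State that inability to do the walk for MS-related reasons is scored as the worst outcome on this endpoint: worst rank, summarised by medians or ranks, or counted as worsened if a proportion is reported.

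The cost is one extra data field and a few sentences, and a rank-based or median summary replaces a simple mean change. The reason code should be in place before the first follow-up visit, because reasons for missed walks are hard to recover afterwards.
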